	
The aim is to assess the fidelity of the intervention especially in patients with cognitive impairment (those at highest risk of HAP) before undertaking a more expensive, larger study.
 
We will also investigate how best to collect the primary outcome for the future study (Antibiotic diagnosis of HAP) and secondary outcome (cost-effectiveness of the intervention).

Outcomes
	
Primary outcome:
 
 • Proportion of delivered mouth care episodes out of eligible mouth care episodes, reported monthly per unit 
Secondary outcomes:
 
Mouth care delivery
 
 • Proportion of delivered mouth care episodes out of eligible mouth care episodes in patients needing consultee consent, reported monthly per unit • Proportion of refused mouth care episodes out of eligible mouth care episodes, per unit per month • Proportion of staff related non delivered mouth care episodes per unit per month • Time to achieve maximal mouth care delivery in each unit (expressed in days) 
Recruitment
 
 • Proportion of recruited patients out of eligible patients per unit monthly • Proportion of patients recruited out of eligible patients needing consultee consent per unit, monthly 
Acceptability
 
 • Acceptability to patients/carers/staff assessed by themes from interviews and observations of mouth care 
Data collection
 
 • Proportion of participants with complete data for cost effectiveness analysis • Proportion of participants with complete records for antibiotic data (as proxy for episodes of HAP) 
At the end of this trial, we will assess specific targets for recruitment, data collection and being able to complete the mouth care intervention to inform whether a larger trial is feasible.

Sample Size
	
A sample size of four clusters has been calculated as being necessary for the

	
feasibility.
 
The future trial is to be a cluster randomised trial, and as such the randomisation units are clusters rather than participants.

Inclusion Criteria	
 1. Aged over 18 years old 2. Admitted to unit in study (predominantly patients with hip fracture, but will include some medical/orthopaedic patients) 3. Consent or assent to take part in the study 4. Anticipated hospital stay of > 3 days

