10. DATA COLLECTION

10.1 Quantitative data collection

10.1.1 Baseline assessments

The study will collect baseline data on all recruited participants prior to them starting the mouth care intervention. This will include oral health assessment data, EQ5D-5L and demographic data. The participant will be asked to complete two EQ5D-5L assessments, one based on how they were one week prior to hospital admission and a second based on how the participant is at the time the data is being collected.

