10.1.2 Demographic, health economic and HAP data collection

During the study we will collect prospective data on all antibiotic prescriptions on all four wards via daily visits by a research nurse. Methods of retrieving antibiotic data across the different wards will be explored. Antibiotic data will be retrieved electronically where possible or prospectively via screening drug cards. For cases of HAP, indication not recorded and source unknown, antibiotic prescriptions may be correlated with clinical notes, and routinely collected clinical, biochemical and radiological data.

EQ-5D-5L data will be collected from all patients, by use of proxy where the patient is unable, at 90 days after discharge. The use of EQ-5D-5L patient reported outcome measures (PROMs) data to provide baseline values will also be investigated (10.1.1). Health care resource utilisation within secondary care will be estimated using the outcome measures listed in Table 3.

Table 3: Data collection for quantitative analysis

Type	Variable	Source	Population	Point of data collection
Recruitment	Number approached Number eligible Number consented Type of consent	Research Nurse/Clinician	All ward patients	At screening / consent
Patient covariates*	Age Sex Diagnosis 4AT Score Rockwood Clinical Frailty Scale	Clinical notes	All recruited participants	At study entry
Primary outcome	Proportion of delivered mouthcare episodes of eligible mouth care episodes, per unit, per month	Mouth care documentation	All recruited Participants	Monthly
Secondary outcomes	Proportion of: Patient refusal Staff related non delivery of intervention Time to maximal mouth care delivery	Mouth care documentation	All recruited participants	Monthly
Staff training	Proportion staff trained in mouth care per unit	Off duty log and research logs	All nurses and health care assistants per unit	Monthly
Efficacy of mouth care intervention	Modified Quigley Hein Plaque Scores	Prospective (by Study team)	A sample of Five patients per site during intervention phase having received minimum twice daily mouth care in preceding 24 hours	Random
Infection outcomes	Antibiotic prescriptions	Prospective (Research Nurse)	All recruited participants	Daily while on ward
HAP outcome data	HAP episodes Have they had a CXR? Y/N Was there a diagnosis of HAP? Obs- highest NEWS on day starting abx WCC/CRP on day starting abx	Clinical notes Webice Vitalpac (or equivalent in each site)	Subset of patients with HAP	Daily while on ward

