12.2 Economic analysis

The feasibility of undertaking an economic evaluation of the previously described mouth care intervention versus usual care will be explored in order to inform a future trial. The economic analysis aims to incorporate the impact of the intervention in terms of potential HAP prevention and the associated costs and outcomes of HAP, i.e. extended length of stay, antibiotic use, and impact on health-related quality of life and mortality. The health economics component of the feasibility study will include consideration of an appropriate evaluation framework, the appropriate instruments, and data collection methods for the cost and outcome data used for the economic analysis. As part of this, the feasibility of collecting economic data via medical records/databases, such as the NHFD and PROMs, will be assessed. An indication of costs associated with the intervention will be provided.

The feasibility of collecting health-related quality of life (HRQoL) data via the EQ-5D-5L (27) will be investigated. EQ-5D-5L data will be collected from all patients, and patients will be asked to describe their health before admission, at admission and 90 days after admission by phone, paper or email; for patients with hip fracture this will be the day before their hip fracture (NHFD 2018). EQ-5D-5L questionnaires will be compared between a subset of patients who developed HAP, and from age-sex matched controls who did not develop HAP. The EQ-5D-5L will be completed by a proxy where the patient is unable to complete the questionnaire themselves. The HRQoL for patients who develop HAP will thereby be compared to the HRQoL for patients who did not develop HAP, in order to estimate the utility decrement associated with HAP.

An NHS costing perspective will be taken for the analysis, with a focus on health care utilisation within secondary care; specifically length of hospital stay for patients who developed HAP versus those who did not develop HAP, obtained via the various hospital databases, including NHFD for participants recruited who have sustain a hip fracture The cost of antibiotics for HAP will also be estimated. Unit costs feeding into the analysis will be derived from established costing sources, such as NHS Reference Costs (28) and the British National Formulary (29).

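### The HAP utility decrement rests on controls matched only on age and sex, so it is likely to be overstated unless cognition and prior health are adjusted for

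*Protocol*

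**What the plan says.** Protocol Section 12.2 fixes the comparison: "EQ-5D-5L questionnaires will be compared between a subset of patients who developed HAP, and from age-sex matched controls who did not develop HAP". Its purpose follows two sentences later: "in order to estimate the utility decrement associated with HAP". No matching factor other than age and sex is named, and no adjustment is mentioned.

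On timing, the same section says "patients will be asked to describe their health before admission, at admission and 90 days after admission by phone". It does not say which of these time points enter the comparison, or whether change from baseline is used. A proxy completes the questionnaire where the patient cannot.

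Other sections bear on the choice:

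- Section 1 (Objectives) singles out "patients with cognitive impairment (those at highest risk of HAP".
- Table 3 in Section 10.1.2 lists, as patient covariates recorded at study entry for every recruited participant, "Age Sex Diagnosis 4AT Score Rockwood Clinical Frailty Scale".
- Section 10.1.1 provides a measure of prior health: "The participant will be asked to complete two EQ5D-5L assessments, one based on how they were one week prior to hospital admission", and a second describing the participant at the time of collection.
- Section 12 leaves the detailed analysis to a statistical analysis plan that is not available here.

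**The concern.** Matching on age and sex removes confounding by age and sex only. If cognitive impairment raises the risk of HAP, as the protocol says, then among patients of the same age and sex those who develop HAP will more often be cognitively impaired. If impairment also goes with lower EQ-5D whether or not HAP occurs, part of the difference between cases and controls was there before the pneumonia.

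Cognitive imbalance also shifts who answers. More cases than controls would have proxy questionnaires, so self-report and proxy report would be mixed unequally. Diagnosis is unmatched too, although the wards take both hip fracture and medical patients and Section 4.1 expects case mix to differ between wards.

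The protocol already holds the variables that would deal with most of this, and pre-admission EQ-5D is the most direct control for prior health. Section 12.2 gives none of them a stated role in the comparison. At stake is the interpretation of the decrement: how much of it reflects HAP, and how much reflects the kind of patient who gets HAP.

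**Working it through.** The protocol gives no decrement, EQ-5D standard deviation, number of cases, control ratio or precision for this comparison, so there is no stated figure to reproduce. What follows is illustrative.

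**Number of HAP cases**

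- The Table 1 recruitment cells sum by site to 504 + 392 + 280 + 135 = 1311, which agrees with the total in Section 5.2.
- The only incidence given is about 1.5% of all in-patients (Section 3): 1311 × 0.015 = 19.7, or about 20 cases.
- These wards may have a higher rate. At an assumed 3% to 10% there would be about 39 to 131 cases.

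**Bias from cognition alone**

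- Prevalence of impairment in controls: p = 0.40, borrowed from the share expected to need a consultee (Section 12.3). Using it as a stand-in for cognitive impairment is an assumption.
- Assumed, not in the protocol: relative risk of HAP with impairment RR = 1.5 to 3; EQ-5D gap between impaired and unimpaired patients g = 0.05 to 0.20.
- Prevalence in cases: RR·p / (RR·p + 1 − p). Bias: (prevalence in cases − p) × g.

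| RR | Prevalence in cases | Bias, g = 0.05 | Bias, g = 0.20 |
|---|---|---|---|
| 1 | 0.400 | 0 | 0 |
| 1.5 | 0.500 | 0.005 | 0.020 |
| 2 | 0.571 | 0.009 | 0.034 |
| 3 | 0.667 | 0.013 | 0.053 |

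**Bias from frailty**

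- All inputs are assumed: Clinical Frailty Scale SD 1.5; odds ratio (OR) for HAP per point 1.2 to 1.5; EQ-5D loss per point 0.05 to 0.10; age and sex balanced by matching; no true effect of HAP.
- For an uncommon outcome, the frailty gap between cases and controls is about ln(OR) × SD².
- OR 1.3, loss 0.08: 0.262 × 2.25 = 0.59 points; 0.59 × 0.08 = 0.047.
- OR 1.2, loss 0.05: 0.182 × 2.25 × 0.05 = 0.02.
- OR 1.5, loss 0.10: 0.405 × 2.25 × 0.10 = 0.09.

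The cognition and frailty figures should not be added, because the two are likely to overlap.

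**Sampling error for comparison**

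- With 1:1 controls and no credit for matching, SE = SD × √(2/n), SD assumed 0.25 to 0.30.
- n = 20: 0.25 × √(2/20) = 0.079; with SD 0.30, 0.095.
- n = 131: 0.031 to 0.037.
- With 20 cases and all other participants as controls (SD 0.25, complete data): 0.25 × √(1/20 + 1/1291) = 0.056. That is about 29% below 0.079, before any gain from adjusting for baseline EQ-5D.

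**The case against.** The strongest reply is that Section 12.2 fixes how controls are chosen but excludes no adjustment. Matching on age and sex and then adjusting for the rest is an ordinary design. Table 3 already labels 4AT, frailty and diagnosis as covariates, and the analysis plan may use them. The text does not limit the comparison to 90 days, so a change-from-baseline analysis is possible. A reader might infer that the protocol disregards these variables, or that the decrement is bound to carry pre-existing frailty. The documents support neither reading: silence is not exclusion, and the protocol names cognition, not frailty, as the HAP risk.

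Other parts of the reply also stand:

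- The illustrative sizes rest wholly on assumed inputs. If frailty rises with age, age matching removes some of the frailty gap, so those figures would be too high.
- The direction is likely but not certain. EQ-5D at 90 days exists only for survivors, and the protocol cites HAP mortality of up to 29% (Section 3) or 70% (Section 1). If the frailest cases die first, surviving cases are selectively fitter and the bias is pulled the other way.
- It is tempting to conclude that the future intervention would look more cost-effective than it is. Section 12.2 does not say that this decrement will be carried into a later model. It rules out a full economic evaluation here and says only that findings will refine later methods.
- It is also tempting to say that most EQ-5D data are thrown away. The subset may simply mean the HAP cases. Only surplus controls go unused, in this one comparison, and the data serve other feasibility aims.

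What the reply does not remove is the residual confounding. The protocol ties the decrement to an age-sex matched comparison while naming a strong risk factor that such matching leaves unbalanced. A standard error larger than the bias is no defence, because confounding does not shrink as cases accrue.

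**Conclusion.** The point holds as a weakness in a stated method. As written, the comparison is likely to overstate the HAP decrement unless cognition and prior health are adjusted for. The expectation about cognition comes from the protocol's own statement of who is at highest risk. That impairment lowers EQ-5D independently of HAP is an assumption, though a modest one.

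The size cannot be fixed from the documents. With few cases the bias may be smaller than the sampling error; with 100 or more it could be comparable with it or larger. If HAP risk were unrelated to cognition and frailty, this bias would be zero.

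The practical weight is limited. The decrement is not a listed outcome, does not enter Table 4, and belongs to an exploratory economic strand. The change is worth making because the better analysis uses data already planned for every participant.

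**What to change.** Amend Section 12.2 so that the main estimate is a regression of 90-day EQ-5D on HAP status in all participants with data, adjusted for pre-admission EQ-5D, 4AT, Clinical Frailty Scale, diagnosis, age, sex and ward. Keep the age-sex matched comparison as a descriptive table, labelled as an unadjusted association. State that the estimate applies to those alive and responding at 90 days, and report deaths by HAP status beside it.

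The model needs one definition of each EQ-5D time point, so two differences should be reconciled. The follow-up is counted from discharge in Section 10.1.2 and from admission in Section 12.2. The prior-health recall is one week before admission in Section 10.1.1, but the day before fracture for hip fracture patients in Section 12.2.

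The cost is a wording change in Section 12.2 and the matching text in the analysis plan, slightly more analysis work, and some loss of participants with missing baseline values. With as few as 20 cases the adjusted estimate will still be imprecise and should be reported with its confidence interval. No new data collection is needed.

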3. BACKGROUND

Hospital acquired pneumonia (HAP) is the commonest healthcare acquired infection, and accounts for 26% of all healthcare associated infections in Europe (1). It is a leading cause of death in hospitalised patients, with a mortality of up to 29% (2). Broad-spectrum antibiotics, used to treat HAP, contribute to the threat of antimicrobial resistance, and consequently have implications for safe healthcare in the near future (3). Patients stay in hospital an average additional 12 days because of HAP (4, 5), and a single day in hospital is estimated to cost £333 locally.

Approximately 1.5% of all hospital in-patients develop HAP (6); on a national scale, the potential individual, economic and system gains from reducing HAP are substantial. The incidence of other healthcare associated infections has been reduced by care units (7). A significant evidence base exists around prevention of ventilator associated pneumonia (8), but two-thirds of patients who develop HAP have never been ventilated (7), and HAP remains an under researched condition.

When people become unwell, particular bacteria (typically Enterobacteriaceae, Staphylococcus aureus and Pseudomonas aeruginosa) become dominant within the microbiome at multiple body sites and pose the risk of secondary infection (9). HAP occurs predominantly due to aspiration of these organisms from the mouth to the lungs (10). Patients are six times more likely to develop HAP if the mouth is persistently colonised by one of these bacteria (11). These bacteria are not usually native to the healthy mouth (12).

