4.2 Setting

Four wards in North East hospitals were chosen due to their having an average length of stay >7 days, which admit patients with hip fracture, over a 15 month recruitment period.

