6.1 Inclusion criteria

1. Aged over 18
2. Admitted to unit in study (wards predominantly with hip fracture patients, but can also include some medical/orthopaedic patients)
3. Consent or consultee approval to take part in the study
4. Anticipated hospital stay of > 3 days

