	Oxygen level/sats on day starting abx			
Other outcome data	Length of stay- acute hospital Death in hospital Death within 30 days EQ-5D at 90 days	Hospital records, contact with participant or consultee	All recruited participants	Once
Discharges/transfers	Discharge Transfer destination Discharge date	Hospital records, contact with participant or consultee	All recruited participants	Once

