12.1 Statistical Analysis

12.1.1 Quantitative data analysis

We will measure and review the primary outcome monthly at each unit. Secondary outcomes relating to recruitment and mouth care episodes will also be collected and reviewed monthly. These will be analysed using simple descriptive statistical techniques, and may be displayed using control charts. Antibiotic use (data collected will include: antibiotic name, dose, frequency and length of course) will be presented with summary statistics. We will compare rates of antibiotic prescribing across trial wards to determine baseline variation and determine timing of antibiotic prescriptions using first day antibiotic prescribed.

For participants moved to community hospitals in Trusts where there is no electronic prescribing, a research nurse will phone the community hospital weekly to check for any prescribed antibiotics. Intra-cluster correlation estimates of outcomes derived from this trial will be compared with those from the SOCLE II trial (26) and used to inform the sample size estimation for a larger trial.

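### Section 12.2 compares length of stay between patients with and without HAP without regard to when HAP began, which biases the excess stay upward

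*Protocol*

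**What the plan says.** Protocol Section 12.2 takes an NHS costing perspective focused on secondary care, "specifically length of hospital stay for patients who developed HAP versus those who did not develop HAP". The same section lists extended stay among the costs and outcomes of HAP that the economic work is meant to capture.

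Table 3 (Section 10.1.2) records the stay as "Length of stay- acute hospital", collected once per participant. It also collects discharge date and transfer destination. Antibiotic prescriptions are collected daily on the ward, and Section 12.1.1 plans to "determine timing of antibiotic prescriptions using first day antibiotic prescribed". Nowhere is that date linked to the comparison of stay. The only matching named in Section 12.2 is on age and sex, and it applies to the EQ-5D-5L comparison.

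Section 3 supplies the figures against which an excess stay would be read: "Patients stay in hospital an average additional 12 days because of HAP (4, 5), and a single day in hospital is estimated to cost £333". Section 12.2 also says that no full economic evaluation will be done here and that the findings will refine the methods of a future trial.

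**The concern.** The two groups are defined by something that happens during the very period being measured. A patient who stays 25 days has many more days on which to acquire HAP than one who stays 5, so the HAP group is enriched with long stayers whatever HAP does. In addition, if HAP starts on day 12, the first 11 days cannot have been caused by it, yet a comparison of whole stays counts them on the HAP side. This is the familiar time-dependent (immortal-time) bias, and it always pushes the estimated excess upward.

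At stake is the excess stay, and hence the cost per HAP case, that this study would hand to the design of the next trial's economic evaluation. An inflated figure would overstate the apparent value of preventing HAP, and the comparison itself would be carried forward as a method.

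**Working it through.** **Inputs from the protocol**
- Mean stay: "average length of stay >7 days" (Section 4.2). No exact mean and no spread are given.
- Entry: "Anticipated hospital stay of > 3 days" (Section 6.1).
- HAP incidence of about 1.5% of in-patients, £333 per bed-day and 12 additional days attributed to HAP (Section 3).
- Planned recruitment 1311 (Section 5.2). Table 1 reproduces it: (56 + 4×112) + (56 + 3×112) + (56 + 2×112) + (45 + 90) = 504 + 392 + 280 + 135 = 1311.
- Expected HAP cases at 1.5%: 1311 × 0.015 = 19.7, about 20.

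**Assumed, because the protocol does not say**
- Mean stay 10 or 14 days, gamma-distributed with shape 3, 2 or 1 (shape 1 is the most skewed).
- HAP possible from day 2, with either a constant daily risk or a risk that decays with a 5-day time constant.
- HAP has no effect on stay, so any difference found is bias.

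**Formula.** For a rare event with constant daily risk from day 2, the chance of HAP is proportional to (T − 2), where T is the stay. If every stay exceeds 2 days, E[T | HAP] − E[T] = Var(T) / (E[T] − 2). With a 3-day minimum, write T = 3 + G, with G gamma of mean (mean stay − 3) and the given shape, so that Var(T) = (mean stay − 3)² / shape.
- Mean 10: 49/3/8 = 2.0; 49/2/8 = 3.1; 49/8 = 6.1 days for shapes 3, 2, 1.
- Mean 14: 121/3/12 = 3.4; 121/2/12 = 5.0; 121/12 = 10.1 days.

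**Simulated difference in mean stay, HAP minus no HAP, with no true effect (5% incidence; 1.5% gives almost the same):**

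| Mean stay | Minimum stay | Onset risk | Shape 3 | Shape 2 | Shape 1 |
|---|---|---|---|---|---|
| 10 days | none | constant | 4.2 | 6.2 | 12.0 |
| 10 days | 3 days | constant | 2.1 | 3.1 | 6.1 |
| 10 days | 3 days | early | 0.8 | 1.2 | 2.2 |
| 14 days | 3 days | constant | 3.4 | 5.1 | 10.1 |
| 14 days | 3 days | early | 0.9 | 1.4 | 2.7 |

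**In money.** With the 3-day minimum the range is 0.8 to 10.1 days: 0.8 × £333 = £266 to 10.1 × £333 = £3,363 per case. Rounding to 1 to 10 days gives about £300 to £3,300. The excess that Section 3 attributes to HAP is worth 12 × £333 = £3,996.

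**Does the remedy work?** A wider set of 72 no-effect scenarios used gamma and lognormal stays with assumed means of 8, 14 and 20 days, coefficients of variation of 0.5 to 1.0, stays truncated at 3 days, and incidence of 1.5% or 10%. The plain difference was positive in all 72, from +0.6 to +21.6 days. Comparing each case with patients still in hospital on the case's onset day gave −0.19 to +0.22 days, which is simulation error around zero.

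Death as a competing end of stay was not modelled.

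**The case against.** The strongest reply is that Section 12.2 names a resource item and two groups but no estimator, and that a time-dependent analysis specified elsewhere would fit its wording. This stands in part: the text does not forbid a valid analysis, and the dates for one are collected. But the comparison is stated, Table 3 records a single stay figure, and nothing ties stay to onset. An analyst following the text as written would obtain the biased contrast. This is a stated comparison to be changed, not a detail left for later.

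The second reply concerns consequence, and it stands. No full evaluation is run, the economic secondary outcome is data completeness, and excess stay appears in no progression criterion in Table 4. About 20 cases would support only an exploratory estimate.

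The third concerns size. A reader might infer that the plan will inevitably show a large spurious excess, on the scale of the 10 to 12 days quoted in the study summary. The documents do not support that. Without a minimum stay and with the most skewed distribution, 12.0 days appears at a mean of 10; the entry criterion makes that distribution doubtful. A 3-day floor at the same mean halves it, and early-clustering HAP reduces it to 1 to 3 days. The floor is itself approximate, because the criterion concerns anticipated stay.

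On Table 3, a reader might infer that most of the stay at hub-and-spoke sites is in a community hospital. Section 7.2.1 says only that the bulk of the intervention is delivered there.

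**Conclusion.** The point holds as a bias of certain direction and uncertain size. A plain comparison of stay between patients who ever had HAP and those who never did overstates the excess due to HAP, even when HAP adds no days. Under the assumptions above (mean 10 to 14 days, 3-day minimum, onset from day 2), the overstatement is about 1 to 3 days if HAP clusters early and about 2 to 10 days if daily risk is constant. The upper end needs highly skewed stays. Stay variance and onset timing are not in the protocol, so no narrower range can be given.

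The practical consequence is moderate. The main risk is that an inflated cost per case, and the method that produced it, pass into the next trial. It is worth correcting because settling methods is the purpose of this study.

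A secondary point also holds. Stay is labelled as acute-hospital stay only, so community-hospital days would be left out where patients are transferred. That could move the estimated excess in either direction.

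**What to change.** In Section 12.2, replace the comparison of length of stay by HAP status with an estimate of excess stay from HAP onset:

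- Date onset by the first day of an antibiotic prescribed for HAP.
- Compare each case's remaining stay with that of patients still in hospital and HAP-free on the same day of stay. Do not exclude comparison patients because they develop HAP later.
- Use a multistate model (in hospital, HAP, discharge or death) instead if the number of cases allows.
- Report the estimate as exploratory, with its confidence interval.
- In Table 3, define stay to final hospital discharge, including community-hospital days, using the transfer destination and discharge date already listed.

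The cost is a few sentences of protocol wording and somewhat more analysis work. No new data item is needed, though onset dates will be less exact where community hospitals are only telephoned weekly (Section 12.1.1). The price is an imprecise estimate, since about 20 cases are expected at 1.5% incidence. The plain comparison rests on the same few cases and is biased as well.
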